4.3 Exclusion criteria

A potential subject who meets any of the following criteria will be excluded from participation in this study:

- Patients with a significant (> 15 of the articular surface) bone fragment on the radiograph.
- Patients with an additional fracture on the ipsilateral hand.
- Patients presenting to the ED with an UCL injury older than 13 days.
- Patients with a history of a UCL injury of the ipsilateral hand.
- Patients with impaired hand function prior to injury due to arthrosis/neurological disorders of the upper limb.
- Polytrauma patients (Injury Severity Score (ISS) = 16 or higher).
- Patients not able to give informed consent.

4.4 Sample size calculation

This sample size calculation is based on our primary endpoint (hand function at 6 months expressed as MHQ score 6 months after injury) and calculated using G Power 3.1.9.2. The MHQ score of an individual without any complaints of the hand is 100. The lowest score, indicating worst pain and severe impairment, is zero. The hypothesis will be assessed using a non-inferiority design. The results from two earlier studies on the subject were used for sample size calculation. [4,5] We used a one-sided significance level of 0.025 and a power of 80% with a standard deviation (SD) of 15, and setting our non-

V7 01-02-2024 12 of 30

inferiority limit at 8. The non-inferiority limit of 8 is based on the previous estimated minimal clinically important difference (MCID) of 15 points, divided by 2 and rounded up to 8. A total of 114 patients will be needed to demonstrate non-inferiority of our hypothesis. Each treatment arm will need 57 patients. Including consideration for a potential 10% loss to follow-up, the total number of patients to be included, set at 114, is multiplied by a factor of 1.10. This results in a total of 126 patients to be included.". The MCID of 15 is based on the average of the MCID's of 23, 13 and 8 for the pain, function and work domains, respectively in patients with carpal tunnel syndrome (CTS). [4] The MCID in MHQ score for patients with thumb injury is not yet investigated. Therefore, we decided to use the MCID of CTS patients.

Considering the uncertain outcome of the control group treatment in terms of MHQ-scores for patients with UCL-ruptures, an independent statistician will assess if the sample size calculation needs adjustment, based on the mean change in MHQ-score and SD in the control group, after half of the patients past their 6-month follow-up (N=28).

V7 01-02-2024 13 of 30

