3. STUDY DESIGN

Multicenter RCT to include 126 patients with 12 months follow-up to compare functional outcomes and cost-effectiveness of cast immobilization with surgical treatment. The study inclusion period is 30 months. Patients will be randomized by simple randomization. A flow diagram of the study is provided in figure 1.

^{**} counted as observed

Figure 1.

V7 01-02-2024 11 of 30

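### The mid-trial sample-size check names an input that cannot change N (control mean change), leaves its SD undefined, and takes that SD from only about half of the available 6-month data

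*Protocol*

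**What the plan says.** Protocol section 4.4 states that the calculation is "based on our primary endpoint (hand function at 6 months expressed as MHQ score 6 months after injury". Its inputs are given as follows: "We used a one-sided significance level of 0.025 and a power of 80% with a standard deviation (SD) of 15", with the non-"inferiority limit at 8". The result is "Each treatment arm will need 57 patients", 114 in total, raised to 126 for loss to follow-up.

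Because the control outcome is uncertain, the same section has an independent statistician assess whether the calculation needs adjusting, "based on the mean change in MHQ-score and SD in the control group", "after half of the patients past their 6-month follow-up (N=28"). As 28 is about half of 57, the check covers half of one arm.

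Related text:

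- Section 3: "Patients will be randomized by simple randomization", so the control count at the look is only about 28.
- Section 6.5: inclusion runs until 114 participants have completed.
- Section 6.7: no early efficacy or futility assessment.
- Section 7: the analysis model adjusts for baseline MHQ.

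**The concern.** The inputs named for the check are not those of the calculation it is meant to check. That calculation needs an SD, a margin, an assumed difference, alpha and power; a control-group mean or mean change is not among them. A large or small mean change could therefore act on N only if someone revisited the margin or the assumed difference mid-trial, and section 4.4 neither describes nor rules that out.

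The SD does belong in the calculation, but because it follows the words on mean change it can be read as the SD of change, which is a different quantity from the SD of 15 used for sizing. It is also to come from one arm, although a similar number of cast patients will have 6-month scores by then. At stake is a final N moved by noise or by the wrong SD: unneeded patients in one direction, a loss of the stated 80% power in the other.

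**Working it through.** **Inputs.** From section 4.4: margin 8, SD 15, one-sided alpha 0.025, power 80%, 57 per arm, 28 controls at the look. Assumed: a true difference of 0, which is not stated but reproduces the plan's figure.

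**1. The plan's own figure.** The normal approximation is n = 2(1.960 + 0.842)² × 15² / 8² = 55.2, so 56 per arm. The noncentral-t version gives 57 per arm (114), power 80.6%. The stated N reproduces.

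**2. Mean change.** It does not appear in the formula. With the margin at 8, N is 114 whatever the control mean change is.

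**3. Which SD.** Assume SDs of 15 at baseline and at 6 months, with correlation r between them (r is not in the protocol, so a range is shown). Then SD of change = 15√(2(1 − r)), and baseline-adjusted SD = 15√(1 − r²). Total N at margin 8:

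| r | SD of change | N | Adjusted SD | N |
|---|---|---|---|---|
| 0.2 | 18.97 | 180 | 14.70 | 108 |
| 0.3 | 17.75 | 158 | 14.31 | 104 |
| 0.5 | 15.00 | 114 | 12.99 | 86 |
| 0.6 | 13.42 | 92 | 12.00 | 74 |
| 0.7 | 11.62 | 70 | 10.71 | 60 |

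The change reading overshoots the planned 114 at low r, agrees with it at r = 0.5 and undershoots it above that.

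**4. Precision of the SD.** If the true SD is 15, the central 95% range of an observed SD is 15√(χ²/df), using the 2.5% and 97.5% points of χ².

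- 28 controls, 27 df: χ² 14.57 and 43.19, so SD 11.0 to 19.0 and N 62 to 180.
- Both arms together, 56 patients, 55 df: χ² 36.40 and 77.38, so SD 12.2 to 17.8 and N 76 to 158.

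**5. Consequence if N followed the estimate.** With a true SD of 15, power is 69.6% at 44 per arm and 70.6% at 45. Power below 70% therefore means N of 88 or less, which follows from an observed SD of at most 13.24. The chance of that is P(χ² ≤ df × 13.24²/15²): 22% with 27 df and 12% with 55 df. For an observed SD of at most 14, which points to N of 100 or less, the chance from 28 controls is 34%; true power at N = 100 is 75%.

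**6. A larger SD in the cast arm.** If the control SD is 15 and the cast SD is 18 or 20 (assumed), the average SD √((225 + SD²)/2) is 16.57 or 17.68. Power at 57 per arm is then 72% or 67%, and the N needed is 138 or 156. A control-only check cannot detect this.

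**7. Cost of lumping the arms.** A true difference d inflates the lumped SD to √(225 + d²/4): 15.13 (N 116) at 4 points and 15.52 (N 122) at 8 points.

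**The case against.** The strongest defence has four parts.

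- **The SD is the correct nuisance parameter.** If the SD of the 6-month score was meant, it matches the sizing calculation. This stands: a reader might infer that the check rests wholly on the wrong parameter, and the text does not support that. Only the mean change has no role; the SD is undefined rather than wrong.
- **Control-only data fit the stated reason for the check.** They reveal no treatment difference, in keeping with section 6.7, and give an unbiased variance estimate if the SD is common to both arms. This also stands: the cost is precision, plus blindness to a larger cast-arm SD, not bias or type I error. But an SD over both arms without codes reveals no difference either.
- **No automatic rule is stated.** The statistician only assesses whether adjustment is needed, section 6.5 runs inclusion to 114 completers, and section 8.3 has amendments notified to the ethics committee. So a planned cut in N should not be read into the text, and the probabilities in step 5 are conditional on N following the estimate. None of this corrects the inputs that section 4.4 names.
- **Direction, cap and formula may sit in an SAP.** Their absence is no finding. The protocol itself, however, fixes the parameters, the arm and the number of patients.

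**Conclusion.** The point holds as a fault in how section 4.4 specifies the check; it does not demonstrate that power will be lost. The control mean change has no route to a new N. The SD is not tied to the 6-month score, and the change reading would give N anywhere from 180 to 70 for r from 0.2 to 0.7; quoting a single r would mislead, since the error vanishes at 0.5 and then reverses. Restricting the check to 28 controls widens the 95% range of N from 76–158 to 62–180 when 114 is right.

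A reader might also compute 11.9 to 20.4 (N 72 to 208) for 28 patients. Those are confidence limits for the true SD when 15 is observed, not the spread of observed SDs when 15 is true, and they do not answer this question.

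The figures assume a true difference of 0, normally distributed scores, a common SD of 15 except in step 6, and N set by the estimate alone. Confidence is medium, because the protocol leaves open which SD is meant and how the result would be used.

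**What to change.** Reword the last paragraph of section 4.4 before the look takes place:

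- **Timing:** when about 57 patients across both arms have the 6-month MHQ.
- **Parameter:** the independent statistician re-estimates only the SD of the 6-month MHQ, over both arms together and without treatment codes.
- **Formula:** the same as at the outset (margin 8, difference 0, one-sided 0.025, power 80%).
- **Limits:** the margin may not change; N may not fall below the planned 114 evaluable patients, in line with section 6.5; any upper cap is set in advance.
- **Deletions:** remove the mean change and the restriction to the control group as inputs. The mean change may be reported descriptively.

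The cost is a wording amendment; the data are collected anyway. There are two downsides. A true difference slightly inflates the lumped SD (15.5, N 122, at 8 points). Pooling also reduces the imprecision without removing it: chance alone can still point to an N of up to about 158, which is why a floor and a preset cap matter.

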5. TREATMENT OF SUBJECTS

5.1 Investigational treatment

INTERVENTION

Patients in the intervention group receive non-operative treatment of the thumb using a cast to immobilize the metacarpophalangeal (MCP) and carpometacarpal (CMC) joint of the thumb in a neutral position for 4 weeks, followed by a removable cast for 4 weeks. During this time frame, the ruptured UCL ligament has a chance to heal. After 4 weeks of immobilization, all patients will be referred for hand therapy. The exact details of the treatment, from first presentation to full recovery, are described step-by-step.

1) First presentation at the ED (pre-treatment protocol)

This pre-treatment protocol applies to patients who present at the ED with a sustained trauma to the thumb, resulting in acute pain and swelling around the MCP joint of the thumb. These patients are potentially eligible for inclusion in the study and receive a temporary cast to immobilize the MCP and CMC joint of the thumb. An appointment with the surgeon is scheduled within 3-5 days from presentation at the ED.

2) First presentation at the outpatient clinic (start intervention)

During the first presentation at the outpatient clinic the surgeon (with sufficient experience in treatment of UCL injuries) confirms the diagnosis complete UCL rupture by physical examination. Laxity of the MCP joint is examined by providing radial force to the proximal phalanx, while stabilizing the thumb metacarpal bone. Stressing the MCP joint in the acute setting may be painful and quarding or muscle spasm may give a false-negative examination. Local anesthesia can be injected into the MCP joint to allow for better examination, when indicated. When the diagnosis of a complete UCL rupture is confirmed (according to the criteria provided under the inclusion criteria), the patient meets the inclusion criteria and has provided informed consent, the patient is randomized. Baseline outcome measures are evaluated in the form of surveys. If feasible at the study site, an ultrasound of the thumb is planned prior to application of a new cast to confirm the diagnosis for study purposes. The outcome of the ultrasound is blinded for the patients as well as for the surgeon. A new cast to immobilize the MCP, in 10-30 degrees (slight) flexion (neutral position), and the CMC joint, in 30-40 degrees palmar abduction, is applied (IP joint is free). Patients will be immobilized for a total period of 4 weeks, including the period between ED and outpatient clinic. After 4 weeks the immobilization cast will be replaced by a removable cast for a period of 4 weeks. Two weeks after the start of immobilization, a second appointment is scheduled to repeat examination of the thumb.

3) Repeat examination at the hand surgery outpatient clinic 2 weeks after ED visit. Laxity of the MCP joint is re-examined by a hand surgeon. The hand surgeon examines if 'tightening' of the UCL has occurred by applying radial deviation stress to the dumb. The chance that re-examination at 2 weeks will induce a re-rupture or a Stener Lesion is close to zero, as re-examination at this time is also part of the current clinical practice in case of

V7 01-02-2024 14 of 30

cast immobilization. 'Tightening' is not a subtle finding and might even be present with less opening during radial deviation stress when compared to the contralateral thumb.

- When the hand surgeon concludes that there is a firm endpoint (meaning adequate healing of the UCL ligament) cast immobilization is continued for another 2 weeks, until a total immobilization period of 4 weeks is completed. An appointment is scheduled after 4 weeks of cast immobilization.
- When there is no firm endpoint of the UCL or there is doubt about a firm endpoint, patients are scheduled for surgery within 5 working days (switching to usual care; see description usual care).

4) Outpatient clinic visit after 4 weeks of immobilization

The patient visits the hand surgeon. The immobilization cast is removed and replaced for a removable cast, which allows the patient to start exercising. Patients are instructed to start using the thumb for regular daily activities, without putting pressure on it, and start thumb exercises consisting of a combination of opposition and abduction/adduction movements. Patients are advised to repeat the exercises 5-10 times a day. A referral is made to the hand therapist to guide this process. Hand therapy will start within 1 week. The frequency and duration of hand therapy will be determined by the hand therapist. Hand therapists from all hospitals will collaborate to achieve consensus on a treatment protocol. Outcome measures are evaluated in the form of physical examination and surveys. A new appointment is scheduled at 3 months.

- 5) Visit to outpatient clinic at 3 months (standard visit)
 Progression of treatment is evaluated with the patient and expectations are managed.
 Outcome measures are evaluated in the form of physical examination and surveys. A new appointment is scheduled at 6 months.
- 6) Visit to outpatient clinic at 6 months (standard visit)
 Progression of treatment is evaluated with the patient and expectations are managed
 Outcome measures are evaluated in the form of physical examination and surveys. A
 new appointment is scheduled at 12 months.
- 7) Visit to outpatient clinic at 12 months (visit for study purpose)

 Treatment outcome is evaluated for study purposes. Outcome measures are evaluated in the form of physical examination and surveys.

USUAL CARE/COMPARISON

The Dutch hand fracture guideline committee recommends operative treatment for patients with a complete UCL rupture, including Stener Lesions, and postoperative management with cast immobilization. [6] Patients will receive surgical treatment of the thumb. Postoperative management consists of cast immobilization of the MCP and CMC joint in neutral position for 4 weeks, followed by a removable cast for 4 weeks. The treatment details, from first presentation to full recovery are described step-by-step.

1) First presentation at the ER (pre-treatment protocol) This pre-treatment protocol applies to patients who present at the ED with a sustained trauma to the thumb, resulting in acute pain and swelling around the MCP joint of the thumb. These patients are potentially eligible for inclusion in the study and receive a temporary cast that immobilizes the MCP and CMC joint of the thumb.

V7 01-02-2024 15 of 30

Patients will be instructed not to use the thumb during this period. An appointment with the surgeon is scheduled within 3-5 days from presentation at the ED.

2) First presentation at the outpatient clinic (start treatment usual care)

During the first presentation at the outpatient clinic the surgeon confirms the diagnosis complete UCL rupture by physical examination. Laxity of the MCP joint is examined by providing radial force to the proximal phalanx, while stabilizing the thumb metacarpal bone. Stressing the MCP joint in the acute setting may be painful and guarding or muscle spasm may give a false-negative examination. Local anesthesia can be injected into the MCP joint to allow for getter examination when indicated. When the diagnosis of a complete UCL rupture is confirmed (according to the criteria provided under the inclusion criteria), the patient meets the inclusion criteria and has provided informed consent, the patient is randomized. Baseline outcome measures are evaluated in the form of surveys. Surgery is scheduled within 5 working days after the outpatient clinic visit. In the meantime, a new cast to immobilize the MCP and CMC joint is applied. If feasible at the study site, an ultrasound of the thumb is planned prior to surgery to confirm the diagnosis for study purposes. The outcome of the ultrasound is blinded for the patients as well as for the surgeon.

3) Surgery

In general, two surgical techniques are described in literature and used in daily clinical practice:

- If the UCL is ruptured in the middle of the ligament, sutures are used to reattach the ligament remnants together.
- When no viable UCL ligaments are present, the UCL is reattached directly to the bone using suture anchors.

Patients can choose between regional anesthetics of the upper arm or complete sedation. The procedure normally takes 30-45 minutes. Postoperatively, patients are treated with a cast immobilizing the CMC and MCP joint for 4 weeks followed by a removable cast for 4 weeks. After 10 days the skin sutures are removed at the outpatient clinic and the cast is renewed. [7]

4) Outpatient clinic visit 4 weeks after surgery
This part of the treatment protocol is identical to the protocol of the intervention group.

5) Visit to outpatient clinic at 3 months (standard visit)
This part of the treatment protocol is identical to the protocol of the intervention group.

6) Visit to outpatient clinic at 6 months (standard visit)

This part of the treatment protocol is identical to the protocol of the intervention group.

7) Visit to outpatient clinic at 12 months (visit for study purpose)
This part of the treatment protocol is identical to the protocol of the intervention group.

V7 01-02-2024 16 of 30

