6.1.2 Secondary study

parameters/endpoints

PATIENT REPORTED OUTCOME (PROM)

Since UCL injuries occur to patients of all ages, the expert panel advised to develop multiple communication channels for providing information and obtaining treatment data. Patients will have the choice to fill in the questionnaires between postal mail and online.

Besides the primary endpoint at 6 months from date of injury, the MHQ will be assessed at randomization, at 4 weeks of immobilization (when the immobilizing cast is replaced by a removable cast) and at 3 and 12 months from date of injury.

Patient-Specific Functional Scale (PSFS) is a self-reported, patient-specific outcome measure, designed to assess functional change, primarily in patients presenting with musculoskeletal disorders. Patients are asked to identify up to five important activities they are unable to perform or are having difficulty with as a result of their problem i.e. putting socks on. In addition to identifying the activities, patients are asked to rate, on an 11-point scale, the current level of difficulty associated with each activity. Following the intervention, patients are asked again to rate the activities previously identified and are given the chance to nominate new problematic activities that might have arisen during that time. "0" represents unable to perform, "10" represents able to perform. Patients select a value that best describes their current level of ability on each activity assessed. The PSFS will be assessed at randomization, after 4 weeks of immobilization (when the immobilizing cast is replaced by a removable cast) and at 3, 6 and 12 months from date of injury.

EQ-5D-5L is a measure of health-related quality of life that can be used in a wide range of health conditions and treatments. The EQ-5D consists of a descriptive system and the EQ VAS. The descriptive system comprises five dimensions: mobility, self-care, usual activities, pain/discomfort and anxiety/depression. The EQ VAS records the patient's self-rated health on a vertical visual analogue scale. This can be used as a quantitative measure of health outcome that reflects the patient's own judgment. The score on the five dimensions can be presented as a health profile or can be converted into a utility score based on an available Dutch scoring algorithm (www.euroqol.org). The area under the curve of utility scores over time will be used to express the effect on quality of life in

V7 01-02-2024 18 of 30

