6.2 Randomization, blinding and treatment allocation

All consecutive patients meeting the inclusion criteria will be asked to participate in the study. After the first outpatient clinic visit informed consent will be obtained by the hand surgeon or the investigator of the study site. Computerized randomization will be performed as soon as written informed consent is provided, with Castor EDC. In trials comparing surgery with non-operative management, blinding of patients and surgeons is not possible and therefore randomization of this study is not blinded.

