expenses by patient and family members (e.g. health related travel, extra private help). The Dutch iMTA Medical Consumption Questionnaire and iMTA Productivity Cost Questionnaire will be adapted to and prepared for the current study setting and disseminated to patients for completion after two, three, six and twelve months of follow up.(11,12) Case report forms or electronic patient dossiers will be used to gather inhospital data. Unit costing will be based on the most recent Dutch guideline on costing in health care research at the time of data analysis. Costing of productivity losses will adhere to the friction costs approach with the current friction period at time of analysis.(13) The base year for costing will be 2022, with unit costs price-indexed if originating from other calendar years.

Patient outcome analysis

Patient outcome analysis in addition to the clinical outcome measures relevant to patients (disability, pain, hand function) the economic evaluation will include the measurement of health status at baseline (within 2 weeks after trauma), at two, three, six and 12 months after injury with the EQ-5D-5L. [15] This questionnaire consists of 5 items, measuring (at 5-point scales) whether patients experience problems, and if so, to what extent with regard to mobility, self-care, daily activities, pain/complaints, and mood. Existing health valuation scoring algorithms (Dutch reference values available through www.euroqol.org) will be used to assign a health utility to each 5-items score pattern. The number of QALYs for each patient will subsequently be calculated by interpolation between successive measurement and determining the area under the curve for the follow-up period of 12 months.

V7 01-02-2024 26 of 30

ETHICAL CONSIDERATIONS

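### Baseline questionnaires are scheduled after open-label randomisation, so the self-reported baseline MHQ in the primary model can be influenced by knowledge of allocation, and the baseline EQ-5D window is inconsistent

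*Protocol*

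**What the plan says.** **Order of steps.** Section 5.1, step 2, cast arm: once diagnosis, eligibility and consent are in place, "the patient is randomized. Baseline outcome measures are evaluated in the form of surveys". The surgery arm uses the same sequence and then turns to the operation: "the patient is randomized. Baseline outcome measures are evaluated in the form of surveys. Surgery is scheduled within 5 working days after the outpatient clinic". Section 6.2 adds that "Computerized randomization will be performed as soon as written informed consent is provided" and that "blinding of patients and surgeons is not possible and therefore randomization of this study is not blinded".

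**Timing in the endpoint section.** Section 6.1.2 says that "the MHQ will be assessed at randomization, at 4 weeks of immobilization" and at later visits. It gives the same baseline moment for PSFS, EQ-5D-5L, NPRS and satisfaction, and dates the short iPCQ to randomisation too. It does not say whether the forms come before or after disclosure of the allocation. It also lets patients choose between paper by post and online completion.

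**Use of the baseline.** Section 7 adjusts the primary mixed model for baseline MHQ, adds a further analysis adjusting 6-month MHQ for baseline differences between arms, and treats PSFS, EQ-5D and pain in the same way. QALYs are an area under the utility curve starting from the baseline EQ-5D.

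**EQ-5D in the economic section.** Under the patient outcome analysis in section 7, the plan is for "the measurement of health status at baseline (within 2 weeks after trauma"). Section 4.3 excludes "Patients presenting to the ED with an UCL injury older than 13 days", so presentation up to day 13 is allowed.

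**The concern.** A covariate in a randomised comparison should be fixed before allocation can touch it. Here the patient may already know whether an operation follows when rating pain, work, satisfaction and function. If that knowledge changes how one arm answers, the arms differ at baseline for a reason that is neither chance nor hand function. The model then corrects the 6-month comparison for a difference that should not be corrected for.

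This matters most for the primary analysis, a non-inferiority claim on a subjective score, where a modest shift either way bears on the conclusion. Change in MHQ from baseline also enters the sample-size reassessment (section 4.4), the ranking of operated patients and the cost-effectiveness outcome (both section 7).

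The EQ-5D wording is a separate matter. Two sections define the same baseline differently, and the looser one can reach past surgery for some patients and close before enrolment for others.

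**Working it through.** **1. The plan's own figure.** Section 4.4 gives SD 15, margin 8, one-sided alpha 0.025 and power 80%. With a true difference of 0, the normal approximation is n = 2 × (15/8)² × (1.960 + 0.842)² = 55.2, so 56 per arm. With the noncentral t, power is 0.799 at 56 and 0.806 at 57, so 57 per arm and 114 in total. Then 114 × 1.10 = 125.4, rounded up to 126. The stated numbers reproduce, and the point below does not change them.

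**2. How a baseline shift enters the primary difference.** With baseline MHQ as a covariate with slope r:

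adjusted difference = (6-month cast − 6-month surgery) − r × (baseline cast − baseline surgery)

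Let a pure reporting effect move one arm's baseline by d points and not carry through to month 6. The bias is then r × d in size. If cast patients report lower at baseline because they know their allocation, the bias favours cast; if they report higher, it goes against cast.

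Assumptions not in the documents: r from 0.3 to 0.5, equal SD of 15 at baseline and 6 months (so that slope equals correlation), and d from 0 to 5. With 57 per arm, SE = 15 × √(1 − r²) × √(2/57). The one-sided error at the margin, if the bias favours cast, is 1 − Φ(1.96 − bias/SE). Power at no true difference, if it goes against cast, is Φ((8 − bias)/SE − 1.96).

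| r | SE | d | bias | error if towards cast | power if against cast |
|---|---|---|---|---|---|
| 0.3 | 2.68 | 0 | 0 | 0.025 | 0.85 |
| 0.3 | 2.68 | 2 | 0.6 | 0.041 | 0.79 |
| 0.3 | 2.68 | 5 | 1.5 | 0.081 | 0.68 |
| 0.5 | 2.43 | 0 | 0 | 0.025 | 0.91 |
| 0.5 | 2.43 | 2 | 1.0 | 0.061 | 0.82 |
| 0.5 | 2.43 | 5 | 2.5 | 0.176 | 0.62 |

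A shift of 2 to 5 points thus gives a bias of 0.6 to 2.5 points, or 0.6/8 = 8% to 2.5/8 = 31% of the margin. With d = 0 nothing happens.

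**3. The EQ-5D window against the visit timetable.** Section 5.1 puts the clinic visit 3 to 5 days after the ED visit and surgery at most 5 working days (about 7 calendar days) later.

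- Patient presenting on the day of injury: surgery by about day 3 + 7 = 10 to day 5 + 7 = 12. The window runs to day 14, so it can include postoperative days.
- Patient presenting on day 13: clinic on day 13 + 3 = 16 to day 13 + 5 = 18, after the window has closed. On this timetable that is already so for anyone presenting on day 12 (12 + 3 = 15).

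**The case against.** The order is read from two adjacent sentences with no connecting word. Section 6.1.2 says only that the forms are taken at randomisation, and the visit table in section 6.3 puts inclusion, randomisation and questionnaires in one row without sequence. A site could well collect the forms first. This stands as a caution about strength, but it does not remove the point: both arm descriptions use the same order, section 6.2 asks for nothing between consent and randomisation, and no section says that the forms must precede disclosure.

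For MHQ, the surgery-arm text places the baseline before the operation, and both arms are in a cast at that visit. So only an expectation or reporting effect is in play, not an early treatment effect. That is correct, and the working above assumes no more.

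Three stronger readings are tempting, and the documents do not support them:

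- **That baseline scores are affected.** The text shows a route, not an effect. It gives no size or direction.
- **That a postoperative EQ-5D baseline is planned.** Section 6.1.2 ties EQ-5D to randomisation, the visit table lists it at the first clinic visit, and section 5.1 puts the surveys before surgery. Only the looser wording in the economic section allows later completion, so this is an inconsistency. Pricing it as a QALY loss would need a utility drop that the protocol does not give.
- **That every late presenter misses the window.** Section 4.1 allows the diagnosis to be confirmed at the ED, so some could be enrolled in time. On the other hand, section 7.2 puts a reflection period of days before consent, which pushes enrolment later.

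**Conclusion.** The point holds as an avoidable route to bias. As written, baseline questionnaires follow open-label randomisation, and the baseline MHQ so obtained is a covariate in the primary model; baseline PSFS, NPRS and EQ-5D are exposed in the same way. The illustrative size is a bias of about 0.6 to 2.5 MHQ points against a margin of 8. It rests on assumed slopes of 0.3 to 0.5, an assumed reporting shift of 2 to 5 points confined to baseline, and equal SDs. The direction is unknown, so the bias could loosen or tighten the non-inferiority test. The true shift may be zero.

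The EQ-5D discrepancy is a textual inconsistency that needs reconciling, whatever the size of any reporting effect.

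**What to change.** - **Sections 5.1 (both arms), 6.1.2 and 6.2:** state that after written consent the patient completes all baseline questionnaires (MHQ, PSFS, EQ-5D-5L, NPRS, satisfaction and short iPCQ), and that only then is randomisation performed or released in Castor. Tie the order to consent, not to a particular visit, because section 7.2 places consent after a period of reflection.
- **Section 7, patient outcome analysis:** replace the two-week window for baseline EQ-5D by completion before randomisation.
- **Patients already enrolled:** record, where it can be established, whether baseline was completed before or after allocation and before or after surgery. Add a sensitivity analysis of the primary endpoint without baseline MHQ adjustment, which a baseline reporting shift cannot bias. Do not simply drop baselines taken after allocation: if sites followed the text, that could be nearly everyone, and same-day dates do not show the order.

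The cost is a form-completion check before randomising and one extra analysis. That analysis is less precise (SE 15 × √(2/57) = 2.81, against 2.43 to 2.68 with adjustment under the assumed slopes), so it is a check on the primary result, not a replacement for it. The sample size stays at 114 evaluable and 126 enrolled, and no treatment step changes.
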